Study Measurements: Participants in both Phase I and II underwent baseline and annual in-center visits for medical history and medication review, anthropometric measures, measurement of renal function (serum Cr for estimation of GFR); other laboratory measures, measures of physical function and health literacy, and other questionnaires. Additionally, they had a follow-up telephone call between annual visits to review medications, update contact information, assess for medical events and hospitalizations. Phase I participants also had an assessment of medical alert accessory acceptance and tolerance. The expected duration of study allows up to 4 annual clinic visits and up to 4 mid-year telephone follow-up visits through June 30, 2016. Beginning, July 1, 2016, annual clinic visits stop and will be replaced with just the annual telephone visit up to December 2021. The mid-year telephone follow-up will stop.

Primary outcomes: CKD-PSIs including medication errors (such as NSAIDs, improperly dosed meds), toxic exposures (such as contrast agents), and medical events (such as hyperkalemia or hypoglycemia); Secondary outcomes: including changing renal function, hospitalization, ESRD, and death. Phase I participants were followed for acceptance and tolerance of medical alert accessory.

- 3 * Describe the relevant prior experience and gaps in current knowledge. Describe any relevant preliminary data:
Refer to Protocol item 5. BACKGROUND

- 4 * Provide the scientific or scholarly background, rationale, and significance of the research and how it will add to existing knowledge:

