

2 If available, upload your applicable literature search:

Name	Created	Modified Date
There are no items to display		

3 * Provide a list of 3 keywords or search terms (1 per line) relevant to your research that would help potential participants find your study using search engines:

Keyword 1: patient safety

Keyword 2: chronic kidney disease

Keyword 3: medical errors

ID: VIEW4E02805A7E400
Name: v2_Supporting Literature

View: v2_Study Procedures

Study Procedures

If you uploaded a separate research protocol document in the 'Research Protocol' page, cite the applicable section and page numbers from that document in the answer boxes below. (If this study is a collaborative UM/VA study please list each procedure that is being conducted and the locations where it is being conducted.)

1 * Describe all procedures being performed for research purposes only (these procedures would not be done if individuals were not in the study) and when they are performed, including procedures being performed to monitor subjects for safety or to minimize risks:

Beginning July 1, 2016, Mod 11 replaces the annual clinic visit with a 10-15 minute telephone call and eliminates the mid-year telephone follow-up visit. In addition, study procedures were also drastically reduced and are now restricted to the following data collection at the annual telephone visit:

- Self-reported safety events leading to hospitalizations/ER visits,
- Death and cause of death,
- Onset of end-stage renal disease requiring renal replacement therapy (dialysis and/or kidney transplant), and
- Updated contact information

Mod 12 adds the Clarke Hypoglycemia Index_Questionnaire_6.20.2016 to the above data collection to measure frequency and severity of hypoglycemic episodes.

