Every effort will be made to complete all visits within target range; however, we anticipate that some participants will miss some annual telephone visits due to unforeseen circumstances, such as illness or family events. At each encounter with the participant, we will attempt to collect all information on events that have occurred since the last encounter and complete data collection. Outlined below are the study procedures and questionnaires.

Participant and Designated Proxy Contact Information - participants will be asked to provide their preferred methods to be contacted, such as mailing address, telephone numbers, and email address. In addition, we will request that the participant provide the contact information of someone we can contact in case we have been unable to reach them, who can provide information to the participant's status, such as moved, ill, hospitalized, or deceased. This information is collected at each annual telephone follow-up visit.

Self-Reported Safety Events Questionnaire - this questionnaire tracks symptoms or medical problems that might be related to self- or medically-directed care and the frequency of hospitalizations.

Clarke Hypoglycemia Index_Questionnaire -Mod 12 adds one additional questionnaire, the Clarke Hypoglycemia Index_Questionnaire. This instrument will be administered beginning July 1, 2016 at the annual, telephone follow-up. Patients with diminished kidney function and diabetes are at risk for hypoglycemic episodes. The Clarke Hypoglycemia Index will provide information about the level of "unawareness" and ability to self-recover and avoid a patient safety event.

2 * Describe all procedures already being performed for diagnostic or treatment purposes (if not applicable to the study, enter "N/A"):

No procedures are being performed for diagnostic or treatment purposes.

3 * Describe the duration of an individual participant's participation in the study:

Mod 11 Changes to be initiated July 1, 2016: Length of participant may extend up to 10 years for those enrolled in 2011 and up to 7 years for the last participants enrolled in 2014.

4 * Describe the duration of the entire study:

Mod 11 Changes to be initiated July 1, 2016: Duration may extend to end of 2021.

5 * Describe any additional participant requirements:

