300 \pm 3.3% \pm 4.7% \pm 5.3% \pm 5.7%

- 2 * Provide the plan for data analysis. Include in the description the types of comparisons that are planned (e.g., comparison of means, comparison of proportions, regressions, analysis of variance, etc.), which is the primary comparison/analysis, and how the analyses proposed will relate to the primary purposes of the study:

From Protocol:

9.I.3. Statistical Analysis

The purpose of this analysis will be to measure the incidence of the CKD-PSIs in the study cohort and to determine the adjusted incidence rates across key factors which relate to safety in CKD. Event ascertainment will begin 4 months (with first telephone follow-up) after enrollment at which time individual events will be recorded longitudinally and cumulatively.

We will consider each specific type of event as an endpoint, but the primary analysis will be based on a composite endpoint of all CKD-PSIs endorsed for inclusion in the trial. The incidence of the events will be expressed per patient-months accrued for all participants in the study cohort and cumulative incidence rates will be determined for both the composite and individual events. Each event will be recorded per individual at the time of the event. For example, if there was an episode of hypoglycemia documented in April for a participant enrolled in January, and an exposure to NSAID in December, then that individual will have 2 CKD-PSI events per 12 patient-months.

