As outlined previously, events will be ascertained from several sources including study visits, medical history review, medication review, and retrieval of hospitalization records. The source of events will be accordingly labeled. Poisson regression will be employed to determine key measured factors which predict the incidence of patient safety events. For this analysis, there will be no predetermined primary exposure to be tested in the regression analysis; however, a key analysis will be the relationship between entry GFR and incidence of CKD-PSIs. Other exposures of interest will be examined. The Poisson regression will assume the number of events for each subject follows a Poisson distribution with mean being a product of the length of the follow-up period and the rate of events, where the logarithm of the expected rate of events (per patient-month), is the linear combination of the covariates. We will check whether data display any over-dispersion and may use negative-binomial regression model if over-dispersion is present.

The data will also be structured such that it is possible to explore the relationship between the incidence of CKD-PSIs and key renal endpoints (secondary outcomes). The key adverse secondary outcomes measures to be examined will be 1) hospitalization and, 2) rate of change in renal function, as measured by estimated GFR. For hospitalization, the primary measure will be incidence of unique hospitalizations over the observed patient-months in each group. Comparisons groups will be the patient-months labeled by the prior incidence or absence of CKD-PSIs in a given patient. While an individual without any CKD-PSI during study observation has a hospitalization, that event occurs in the non-PSI group, another individual with at least one CKD-PSI in the study period who has two hospitalizations – one before and the other after the incidence of the CKD-PSI – will contribute two hospitalization events to the data set. The first will be assigned to the non-CKD-PSI group and corresponding to the period from entry to the occurrence of the first CKD-PSI, the second event will be assigned to CKD-PSI group and corresponding to the period from the occurrence of the first CKD-PSI to last follow up time or the end of the study.

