Generalized estimating equations (GEE) with log link function will be employed for examination of the relationship between incidence of CKD-PSIs and hospitalization. GEE will allow for joint modeling of the repeated measures and the incorporation of such a time-varying covariate based in the detection of a CKD-PSI. The effect of ever experiencing CKD-PSI during the study period on the frequency of hospitalization will be displayed by the rate ratio and its 95% confidence interval of hospitalization in PSI group versus non-PSI group.

Estimated GFR will be determined at baseline and at all annual follow-up visits. Since enrollment will be planned to ensure at least one follow-up visit per individual, it will be possible to generate slope estimates for change in renal function in all study participants. Measurement of serum creatinine will be done at a single laboratory to minimize variation in calibration across laboratories, and GFR will be estimated with the modified MDRD equation. Proper transformation will be performed as needed if the distribution of GFR values is skewed. Random effects models will be used to compare change in GFR between those with and without a CKD-PSI. To employ random effects models as a means to compare change in renal function between those participants with and without the incidence of a CKD-PSI and adjust for multiple covariates, the following assumptions will be made:

Each individual will have a separate slope β_i , with an independent intercept α_i , and an error term ϵ_i with mean 0 and a Normal distribution. The residual variance of each slope is assumed to be the same across all individual slopes and the distribution of β_i for participant time assigned to each group is assumed to be a Normal distribution with a mean of b_1 or b_2 corresponding to the two groups (without or with the bracelet/necklace). Similarly, the distribution of individual intercept α_i is assumed to be a Normal distribution with an equal variance across all individuals, and a mean of a_1 or a_2 corresponding to the two groups.

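### Section 9.I.3 sets no cut-off at 1 July 2016, so the primary CKD-PSI rate as written mixes full ascertainment with up to 5.5 years of one annual self-report call

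*Combined protocol and SAP*

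**What the plan says.** Section 9.I.3 (Statistical Analysis) takes the composite of all endorsed CKD-PSIs as primary. On the denominator it says: "The incidence of the events will be expressed per patient-months accrued for all participants in the study cohort". In the Poisson model each subject's event count has "mean being a product of the length of the follow-up period and the rate of events". On sources: "events will be ascertained from several sources including study visits, medical history review, medication review, and retrieval of hospitalization records". Each event's source is to be labelled, but no planned analysis uses the label. The same section still assumes the visit schedule: "Estimated GFR will be determined at baseline and at all annual follow-up visits".

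Research Design, item 2, describes collection up to 30 June 2016. There was an annual clinic visit with medication review and laboratory measures, plus a "follow-up telephone call between annual visits to review medications, update contact information, assess for medical events and hospitalizations".

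Study Procedures, item 1, changes this from 1 July 2016. Under Mod 11 "study procedures were also drastically reduced and are now restricted to the following data collection at the annual telephone visit": the participant's own report of safety events that led to a hospital stay or emergency visit, death and its cause, onset of ESRD, and contact details. Mod 12 adds the Clarke questionnaire "to the above data collection to measure frequency and severity of hypoglycemic episodes", which the Lay Summary limits to participants with diabetes. The mid-year call stops, and under item 5 medication containers and the diary are no longer kept. Follow-up may run to the end of 2021.

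**The concern.** The primary rate needs a numerator and denominator that go together: patient-months should count only while the events in the composite can be detected. The composite in Research Design, item 2, includes NSAID use, wrong dosing, contrast exposure, hyperkalemia and hypoglycemia. From July 2016 the first four lose most of the sources that 9.I.3 relies on, unless they led to hospital or emergency care or the participant volunteers them. The patient-months continue to accrue.

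The resulting figure would reflect how much follow-up falls after June 2016 as well as how often CKD-PSIs occur. Its make-up would differ between early and late enrollees. The exposure label in the hospitalization analysis is affected too, because time after an undetected CKD-PSI stays in the comparison group, although this effect is secondary.

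**Working it through.** The plan gives no figure for this point. Table 4 gives half-widths for a one-year proportion (±5.6 points at n = 250 and 30%, which a Wald interval reproduces at 5.68). It does not address a multi-year rate in 350 participants.

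**Documented inputs.** The reduced period, July 2016 to December 2021, is 5.5 years. Total follow-up is at most 10 years (2011 enrollees) and at most 7 years (last 2014 enrollees) (Study Procedures, item 3). N = 350. For illustration the event rate is 30% per year, the 9.I.4 figure for medication errors.

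**Assumed inputs, not in the documents.** The share f of CKD-PSIs still captured after June 2016 is 0.25, 0.5 or 0.75. The true rate is constant. Average time before July 2016 is 3.5 years (3.0 as a check). Attrition is 10% per year (none as a check). The start of event ascertainment 4 months after enrolment is ignored.

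**1. Share of reduced time at full length.** 5.5/10 = 55% for 2011 enrollees and 5.5/7 = 79% for the last 2014 enrollees. With observed/true = 1 − w(1 − f), where w is that share, f = 0.5 gives 1 − 0.55 × 0.5 = 0.73 and 1 − 0.786 × 0.5 = 0.61. The same true rate would read differently by enrolment date.

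**2. Cohort average with 10% attrition.** Let l = −ln(0.9) = 0.10536.
- Time before: (1 − e^(−3.5l))/l = 2.93 years.
- Time after: (e^(−3.5l) − e^(−9l))/l = 2.89 years.
- w = 2.89/(2.93 + 2.89) = 0.4965.
- Observed/true for f = 0.25, 0.5, 0.75: **0.63, 0.75, 0.88**.
- Shortfall at 30% per year, 30w(1 − f): 11.2, 7.4, 3.7 points.

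**3. Sensitivity.** With no attrition, w = 5.5/9 = 0.611 and the ratios are 0.54, 0.69, 0.85. With 3.0 years before and 10% attrition, w = 0.542 and the ratios are 0.59, 0.73, 0.86.

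**4. Could the Clarke questionnaire offset the loss?** Treat 14.8% (hypoglycemia) and 30% (medication error) as yearly rates of a two-part composite. If a share c of medication errors is still captured, hypoglycemia counts must be multiplied by (44.8 − 30c)/14.8 for no net change. That is 2.0, 2.5 or 3.0 for c = 0.5, 0.25 or 0. The check is rough, because 9.I.4 gives these figures as percentages of participants affected, while 9.I.3 counts every event.

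**5. Precision cost of a 30 June 2016 cut-off (10% attrition, f = 0.5).**
- All follow-up: 350 × 0.30 × (2.93 + 0.5 × 2.89) = 459 events; 1.96/√459 = 9.1%.
- To 30 June 2016: 350 × 0.30 × 2.93 = 307 events; 1.96/√307 = 11.2%, or 3.4 points on 30%.
- With no attrition: 656 against 367.5 events, 7.65% against 10.2%.

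**6. When would pooling still be better?** Equate mean squared errors: [0.30w(1 − f)]² + 0.30(2.93 + 2.89f)/(350 × 5.81²) = 0.30/(350 × 2.93). The solutions are f of about 0.92 and 1.08. If over-dispersion makes both variances four times larger, they are about 0.83 and 1.16. Pooling is better only between those values.

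**The case against.** The strongest reply is that 9.I.3 is an excerpt from a separate protocol that was not supplied, and that its denominator sentence speaks of all participants, not all follow-up time. Since the section ties events to visits and medication review, it might mean patient-months under that schedule only. This stands as a caution: a cut-off may exist elsewhere. In the text supplied, however, exposure is the length of follow-up, the hospitalization analysis runs to last contact or study end, and the study may extend to the end of 2021. Including the telephone-only months is the natural reading. The surrounding form was updated with final sample sizes and Mod 11/12 procedures, while 9.I.3 was not.

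The second reply concerns capture. Study Procedures, item 1, says staff will try at each contact to gather everything that has happened since the last one. It also describes the self-report form broadly: "this questionnaire tracks symptoms or medical problems that might be related to self- or medically-directed care and the frequency of hospitalizations". NSAID use or a contrast scan could be reported that way, and Clarke-reported episodes could raise hypoglycemia counts. This stands in part. It does not restore laboratory data or medication review, but it leaves f unknown and the net direction open.

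Third, a cut-off at each participant's last clinic visit would lose mid-year-call and hospital-record events. It would also lose the final interval of anyone who died, reached ESRD or dropped out between visits, so truncation would depend on outcome. This stands, and a common calendar date avoids it.

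**Conclusion.** The mismatch is documented and should be fixed. As written, the primary composite rate and the Poisson exposure pool two ascertainment regimes, and the mix depends on enrolment date. Understatement is probable, because medication errors, outpatient toxic exposures and laboratory-detected hyperkalemia lose most of their listed sources. The ratios 0.63, 0.75 and 0.88 illustrate possible size; they rest on assumed capture, attrition, time before July 2016 and a constant true rate, and are not estimates.

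A reader might infer more than the documents support:
- That the rate is shown to be too low. Retained capture is not stated, nor whether Clarke-reported episodes count as CKD-PSIs.
- That the bias exceeds the precision in Table 4. That table concerns a one-year proportion and is not a yardstick for this rate.
- That a Phase I versus Phase II comparison is compromised. 9.I.3 plans no such contrast in CKD-PSIs.
- That the entry-GFR association is biased in a known direction. It would be distorted only if the share of telephone-only time or the capture varies with GFR, which the documents do not show.

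**What to change.** State in 9.I.3 that, for the primary composite rate, the Poisson or negative-binomial regression and the CKD-PSI exposure label, events and patient-months are both counted only to 30 June 2016, or to earlier death or loss to follow-up. Events from mid-year calls and hospital records up to that date are included. If the full protocol already has such a rule, repeat it here.

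For later data:
- Report self-reported safety events and Clarke hypoglycemia separately, using the source labels already planned.
- Relate later hospitalization, ESRD and death to CKD-PSI status fixed at 30 June 2016, as a separate analysis.
- Keep two sensitivity analyses: a full-follow-up model with a before/after July 2016 period term, and a cut-off at the last clinic visit.

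The change is wording only and discards no data. The price is fewer patient-months: in the illustration at 30% per year and 50% capture, about 307 events instead of 459, and a relative 95% half-width of about 11.2% instead of 9.1%. In that scenario it removes a shortfall of 7.4 points. If capture is in fact nearly complete, the lost precision buys little, and the period-term model will help to show this.

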A clinical trial is a research study in which one or more human subjects are prospectively assigned to one or more interventions (which may include placebo or other control) to evaluate the effects of those interventions on health-related biomedical or behavioral outcomes.

Yes No

ID: VIEW4E0280569E000
Name: v2_Type of Research

Lay Summary

- 1 * Provide a summary of the background and purpose of the study in language that can be understood by a person without a medical degree.

Chronic kidney disease not requiring dialysis (CKD) is common, but under-recognized, among patients who frequent the health care system, where improving patient safety is a high priority. Poor recognition of the disease and several other features unique to CKD make it a high-risk condition for adverse, patient-safety incidents (PSIs). In this context, PSIs refer to events of unintended harm or injury related to medications or medical care. These adverse safety events may include those usually cited for the general population (PSI), but also, CKD-specific unsafe practices (CKD-PSI) all of which, in turn, can lead to frequent hospitalization, accelerated loss of kidney function, increased risk of end-stage renal disease (ESRD), and death - all common outcomes in CKD. CKD-PSIs have been established in prior work by the PI with the help of an expert panel but it is not known how commonly PSIs or CKD-PSIs occur or how to possibly measure these reliably in the CKD population. Furthermore, it is not known what role poor disease recognition plays in the occurrence of such safety events. Finally, it remains to be determined whether CKD-PSIs contribute to the high frequency of adverse outcomes so common in this disease. If CKD-PSIs are common and account for a significant portion of the adverse events so common in this population, then it is possible that by reducing the incidence of CKD-PSIs, through increased disease recognition, outcomes can be improved in this patient population.

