Name: v2_Lay Summary

View: v2_Justification, Objective, & Research Design

Justification, Objective, & Research Design

If you uploaded a separate research protocol document in the 'Research Protocol' page, cite the applicable section and page numbers from that document in the answer boxes below.

- 1 * Describe the purpose, specific aims, or objectives of this research. State the hypothesis to be tested:

In this study, 371 individuals with pre-dialysis CKD were consented to achieve a cohort of 350 that proceeded to study procedures with the following objectives:

1) Assess the Tolerability and Efficacy of a Commonly-used Medical Alert Accessory Designed to Increase Recognition of Chronic Kidney Disease (CKD) in a Pilot Sample of Participants from the SAFE KIDNEY CARE COHORT

The first 108 subjects of the Safe Kidney Care cohort (Phase I) were provided a medical alert accessory (choice of bracelet or necklace, stainless steel or sterling silver). Regular contacts were made with Phase I participants to monitor tolerance of medical alert accessory along with the use of a supplemental informational website on best safe practices for patients with CKD, and to measure the frequency of newly-developed Patient Safety Indicators specific to CKD (CKD-PSI).

2) Validate Established CKD-PSIs in a Cohort of Individuals with CKD Tracked Longitudinally

After enrollment in Phase I has concluded, an additional 242 volunteers from the target population were enrolled into the Safe Kidney Care cohort (Phase II) for a total of 350 participants tracked longitudinally to detect the incidence of established CKD-PSIs, assess their measurability, and exam the relationship between the occurrence of these safety events and adverse renal outcomes.

- 2 * Discuss the research design including but not limited to such issues as: probability of group assignment, potential for subject to be randomized to placebo group, use of control subjects, etc.:

Study design: Observational cohort study. Study population: Persons with Stage III – V, pre-dialysis CKD enrolled from a single center (n = 350). The first 108 participants (Phase I) were provided a medical alert accessory (choice of bracelet or necklace).

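### Assessing the measurability of CKD-PSIs is part of objective 2 and each event's source is to be labelled, but no analysis in the supplied section 9.I.3 uses the label

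*Combined protocol and SAP*

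**What the plan says.** The Lay Summary gives measurement as one reason for the cohort: "it is not known how commonly PSIs or CKD-PSIs occur or how to possibly measure these reliably in the CKD population". Objective 2 (Justification, Objective, & Research Design, item 1) then sets three tasks for the 350 participants: "to detect the incidence of established CKD-PSIs, assess their measurability, and exam the relationship between" these events and adverse renal outcomes.

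Section 9.I.3 (Sample Size and Data Analysis, item 2) describes ascertainment: "events will be ascertained from several sources including study visits, medical history review, medication review, and retrieval of hospitalization records". It adds: "The source of events will be accordingly labeled". The aim of the analysis is to "measure the incidence of the CKD-PSIs in the study cohort and to determine the adjusted incidence rates across key factors" related to safety, and "the primary analysis will be based on a composite endpoint of all CKD-PSIs endorsed for inclusion in the trial". Each event type is also to be reported as its own endpoint.

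From 1 July 2016 (Study Procedures, item 1), clinic visits and mid-year calls end. Collection is limited to one yearly call of 10 to 15 minutes. The call covers self-reported safety events that led to a hospitalization or ER visit, death, ESRD and contact details, with the Clarke hypoglycemia questionnaire added by Mod 12.

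**The concern.** Labelling each event by source is the step that would let the study say how measurable an indicator is: which source finds it, how often a second source confirms it, and how far the count depends on where one looks. The supplied plan takes that step and then makes no use of it. It also does not define measurability or say how an event found by two sources is counted.

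Two things are at stake. First, the study could report a rate for each CKD-PSI without saying how dependably it was detected, although objective 2 is presented as a validation. Second, ascertainment narrows sharply on 1 July 2016, and 9.I.3 does not say how later follow-up enters the incidence analysis. If all follow-up time went into one rate, a change in detection could look like a change in safety.

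**Working it through.** **1. The plan's own figure.** Table 4 is the only quantitative design statement. The half-width is 1.96 × √(p(1−p)/n). For n = 250:

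| Incidence p | Computed | Table 4 |
|---|---|---|
| 10% | ±3.72 | ±3.6 |
| 20% | ±4.96 | ±4.8 |
| 30% | ±5.68 | ±5.6 |
| 40% | ±6.07 | ±6 |

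The differences are 0.07 to 0.16 points, so the table is not in dispute. It covers sampling error only and says nothing about events missed by a source.

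**2. Objective 2 against the supplied 9.I.3.**

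| Part of objective 2 | Analysis in 9.I.3 |
|---|---|
| Incidence of CKD-PSIs | Rates per patient-month and cumulative incidence, composite and by type; Poisson or negative-binomial regression |
| Measurability | None |
| Relation to renal outcomes | GEE for hospitalization; random-effects models for GFR slope |

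The sentence on labelling is the only mention of the label. No yield by source, agreement, confirmation rate or rule for duplicates follows.

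**3. Ascertainment before and after 1 July 2016.**

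| | To 30 June 2016 | From 1 July 2016 |
|---|---|---|
| Contact | About every 6 months (annual visit, mid-year call) | One call a year |
| Medication review | Yes | Not listed |
| Laboratory measures | Yes | Not listed |
| Hospital records | Named as a source | Not listed; ending not expressly stated |
| Self-report | Implied, since the Lay Summary says the call continues this capture | Events leading to hospitalization or ER visit |
| Clarke questionnaire | No | Yes, for hypoglycemia |

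The later period is long. July 2016 to December 2021 is 5.5 years. Study Procedures, item 3 allows up to 10 years for 2011 enrollees (5.5/10 = 55%) and up to 7 for the last 2014 enrollees (5.5/7 = 79%). So 55% to 79% of maximum potential follow-up falls in the reduced period.

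**4. Would a source comparison be informative?** Inputs are the 350 participants and the yearly figures in 9.I.4: 14.8% with hypoglycemia and 30% with a medication error. Assume one event per affected participant, one year of data, and an agreement proportion a of 50% to 90%. The assumed values are not in the documents.

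- Affected participants m: 350 × 0.148 ≈ 52, and 350 × 0.30 = 105.
- Half-width: 1.96 × √(a(1−a)/m).

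| m | a = 50% | a = 70% | a = 90% |
|---|---|---|---|
| 52 | ±13.6 | ±12.5 | ±8.2 |
| 105 | ±9.6 | ±8.8 | ±5.7 |

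If only half of the 52 could be compared (m = 26), the half-width at a = 50% is 1.96 × √(0.25/26) = ±19.2 points. The comparison is therefore feasible for common classes and imprecise for rare ones.

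**The case against.** **The data would still exist.** This stands. A reader might infer that measurability cannot be reported at all. The documents do not support that, because a source recorded per event can be tabulated at any time. What is missing is a definition and a prespecified analysis.

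**The rest of the protocol may cover it.** Only 9.I.3 and 9.I.4 are reproduced, and 9.I.3 refers back to an ascertainment description that is not supplied. The omission can be asserted only for the supplied plan.

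**Measurability is undefined, and overlap between sources is partly inferred.** This also stands. Self-report is not named in the 9.I.3 list, and no section says every class is sought in every source. Yield by source applies to all classes; agreement applies only where two sources cover a class.

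**Calibrating the telephone-only years.** A reader might infer that those years can never be bridged to the earlier ones, or that the overlap period would supply a correction factor. Neither is supported. Some overlap is implied, but on 1 July 2016 the recall interval roughly doubled, the diary and the retention of medication containers ended (Study Procedures, item 5), and the scope of events narrowed. Self-report performance before that date need not carry over. Capture-recapture has a related weakness: the documents do not say whether records were sought because a participant reported an admission, so independence of sources cannot be assumed.

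**A figure for the loss.** A reader might assume 80% detection by records and 40% to 80% by self-report. With independence, the two together find 1 − 0.2 × (1 − s), which is 88% to 96%, and self-report alone would lower the count by 55% to 17%. Without independence, the two together find between 80% and 100%, and the fall ranges from 0% (1 − 0.8/0.8) to 60% (1 − 0.4/1.0). No input comes from the documents, so no such figure should be attached to this study.

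**Conclusion.** The point holds as a gap in prespecification. One of the three stated parts of objective 2 has no result if the supplied 9.I.3 is followed exactly, although the plan already calls for the label needed to produce one. Incidence in the multi-source period can still be estimated; what is lacking is evidence on how dependably each indicator is detected. No size of bias is claimed. The feasibility figures (about ±6 to ±14 points from 52 to 105 affected participants) rest on the assumptions stated with them.

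The telephone-only years are a related reporting matter. Their listed content is too narrow for the composite to be comparable with the earlier period. This reads the restriction to telephone items as complete, which is reasonable but not expressly stated for hospital records.

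**What to change.** Add to 9.I.3, for the period to 30 June 2016 and by CKD-PSI class:

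1. A table of event yield by source, with an event found by two sources counted once.
2. A cross-tabulation of self-report against hospital record or medication review within the same inter-visit window. Report the percentage confirmed (positive predictive value) with a 95% confidence interval. Report sensitivity only where the reference source was sought independently of self-report.

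Report incidence for the multi-source period separately from the telephone-only years. State that the later safety-event data list only self-reported events leading to hospitalization or ER visits plus the hypoglycemia questionnaire, and are not comparable for the composite. Fix the reference source and the matching window before looking at the data, since choosing them afterwards would weaken any claim of validity.

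The cost is SAP wording and a modest extra analysis of labels already planned, with no new data collection. The agreement estimates will be imprecise for rarer classes and limited to classes covered by more than one source.
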